1.2. Funding

This study is funded by the National Institute for Health Research's Programme Grant for Applied Research titled 'Developing primary care services for stroke survivors' reference PTC-RP-PG-0213-20001. The chief investigator for the study is [name].

IRAS: 233891

Background: No formal primary care based model of care exists to support stroke survivors living in the community. A large variation in the range, quality and access to health services offered to stroke survivors between and within local primary care trusts suggests that many of the stroke survivors' needs are not being met systematically. Therefore, to address the longer term needs we have developed a multi-factorial primary care model that seeks to enable greater engagement with stroke care and community services, to link effectively to specialist services, and to improve the lives of stroke survivors.

Aim: To evaluate the clinical and cost effectiveness of a novel model of primary care for stroke survivors living in the community.

Method: The IPCAS Trial is a two-arm cluster randomised controlled trial with general practices as the unit of randomisation. People on the stroke registers of GP practices in the East of England and the East Midlands will be invited to take part. We will aim to recruit 920 people with a history of stroke registered with 46 general practices.

Analysis: The primary endpoint for the trial will be two sub-scales (emotion and handicap) of the Stroke Impact Scale (SIS v3.0) as co-primary outcomes at 12 months (adjusted for baseline).

4. Background and Rationale

Survival after stroke is improving^{1,2} which means the longer-term care of people with stroke is going to play an increasingly important part of population based stroke care. Surveys demonstrate that the longer term needs of people with stroke and their carers are not being adequately addressed and that the majority of stroke survivors are dissatisfied with care after discharge from hospital.^{3,4} Two of the themes that run through these surveys are information needs (54% of respondents to the national Stroke Association survey reported wanting more information about stroke) and feelings of abandonment (42% of respondents to a Stroke Association survey reported feeling abandoned after leaving hospital).³ Other important themes include the emotional and social impact of stroke in addition to the many physical and cognitive sequelae of stroke including memory and concentration problems and fatigue.⁵

The longer term problems faced by people with stroke and their carers have been highlighted in recent national reports such as the National Audit Office report 'Progress in Improving Stroke Care' (2010)⁴ and the Department of Health Cardiovascular Disease Outcomes Strategy (2013).⁶ Approximately a third of stroke survivors are left with moderate to severe levels of disability at 6-months⁷. However, evidence for how best to support long-term stroke survivors is sparse⁸ especially beyond the first year after stroke⁹. Recent trials of greater specialist input for specific tasks such as speech and language therapy and occupational therapy have not demonstrated patient benefit^{2,8}.

Primary care could play an important role in the care of people with stroke, supporting access to community services, facilitating transfer back to specialist services when new problems emerge, education about stroke and provision of information, and continuing to manage those aspects of care that are traditionally managed in primary care (for example, risk factor management and psychological issues). However, the feeling of 'abandonment' of people with stroke after hospital discharge suggests this role is not always being fulfilled. Despite the recommended annual and structured health and social care review at six months and 1 year after the stroke¹⁰, in reality the majority of survivors do not have a structured review of needs beyond the first six weeks after discharge¹¹.

At present no formal primary care based model of care exists to support stroke survivors living in the community. There is a large variation in the range, quality and access to health services offered to stroke survivors between and within local primary care trusts¹². To address the longer term needs we have developed a multi-factorial primary care model that seeks to enable greater engagement with stroke care and community services, to link effectively to specialist services, and to improve the lives of stroke survivors.

5. Aims and Objectives

5.1. Aim

To evaluate the clinical and cost effectiveness of a novel model of primary care for stroke survivors living in the community.

5.2. Objectives

- To assess the clinical effectiveness of the new model of primary care for stroke survivors compared with standard care. The primary endpoint for the trial will be two sub-scales (emotion and handicap) of the Stroke Impact Scale (SIS v3.0)¹³ as co-primary outcomes at 12 months (adjusted for baseline).
- To assess the long-term cost effectiveness of the new model of primary care for stroke survivors compared with standard care.

6. Methods

6.1. Design

The IPCAS Trial is a two-arm cluster randomised controlled trial with general practices as the unit of randomisation.

6.2. Trial Population

People with a history of stroke on the registers of GP practices in the East of England and the East Midlands will be invited to take part. We will aim to recruit approximately 920 people registered with 46 general practices. We will aim to evaluate the primary care model in contrasting catchment areas to reflect the different demographic characteristics of the general population.

6.2.1. Inclusion Criteria

- On practice register with a history of stroke
- Able to provide written informed consent (with or without the help of a carer)
- Age 18 years or older

6.2.2. Exclusion Criteria

- Patients on the palliative care register
- Living in a nursing home

6.3. Recruitment

6.3.1. GP Practices

Practices from the East of England and the East Midlands will be recruited in collaboration with the local Clinical Research Networks (CRNs), who will identify interested practices representing a range of urban/rural and different socio-economic status. We will target Practices with a stroke register comprising a minimum of 100

patients, to ensure that we reach our cluster target of 16 – 24 participants (see appendix B).

6.3.2. Stroke Survivors

Prior to randomisation at practice level (see below) electronic searches of the clinical computer system will generate a list of people on the register with a history of stroke who meet the inclusion criteria for the study.

Potentially eligible participants will be sent an invitation to take part in the study. The invitation pack will contain an invite cover letter, the Patient Information Sheet (PIS), a consent form, a questionnaire containing the primary outcome, and instructions to return the consent form and questionnaire to the researchers in a pre-paid envelope (provided). If no response is received within 2 weeks from the initial mail-out, the Practice will send a reminder. If no response is received after a further 4 weeks, no further attempts at contact will be made.

6.4. Randomisation

Once all invitation letters and reminders have been sent out to patients in a practice, the GP practice will be randomised to intervention or control (ratio of 1:1). Randomisation will be performed using a stratified, random permuted block design. The stratification factor will be GP practice size, split into two levels: $\leq 10,500$ and >10,500 patients.

Randomisation will be performed centrally by the study team who will then inform each practice about their allocation.

7. Interventions

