9.1. Baseline Data Collection

The primary outcome data will be collected via postal questionnaire at the time of invite to the study prior to Practice randomisation. Secondary outcome data (SIS Short Form, EuroQol EQ-5D-5L, and ICEpop CAPability measure for Adults (ICECAP-A)) will also be collected by postal questionnaire after randomisation. Non-responders to the secondary outcome questionnaire will be followed-up by telephone. Where a patient has difficulty completing a questionnaire because of physical or communication difficulties, they will be encouraged to seek the help of a carer.

Demographic data including age, ethnicity, gender, time since stroke, partial post code, and co-morbidity and medication use (prescription & 'Over the Counter', OTC) will also be collected at baseline.

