# 6 Study Methods

#### 6.1 General Study Design and Plan

The IPCAS trial is an open-label, two-level cluster randomised trial of patients clustered within general practices, with randomisation occurring at the level of the general practice.

General practices are randomised in a ratio of 1:1 to the control or experimental group. General practices in the control arm offer standard care to their patients. General practices in the experimental arm offer a novel model of care to their patients. Once all invitation letters and reminders are sent out to patients in a general practice, the general practice can be randomised.

Randomisations are performed using a stratified, random permuted block design. The stratification factor is general practice list size, split into two levels based on the approximate median general practice list size for the geographic areas likely to be included in the trial. The two strata levels are:

- i) Strata 1: General practice list size less than 10,500 patients;
- ii) Strata 2: General practice list size equal to or greater than 10,500 patients.

Random permuted blocks are used in order to maintain close balance in the allocation of the two treatment groups within each strata, and to minimise opportunities for selection bias. The exact block sizes used to produce the randomisation lists is documented separately by the statistician in order to help maintain blinding.

The sequence of key study points is summarised in the following flow chart.

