#### 8.2.1 Full Analysis Population

The full analysis population, also often referred to as the "intention-to-treat" population, comprises all randomised general practices and consented patients within them, regardless of eligibility error, post-randomisation withdrawal, and whether the assigned treatment was received, with sufficient or insufficient compliance. Any analyses will be based on the treatment arm assigned at randomisation, regardless of what treatment was actually received.

A subset of the full analysis population will be used to analyse the two co-primary efficacy end-points, including only the patients with the necessary data available at baseline and twelve months.

The full analysis population will also be used to analyse several secondary and exploratory end-points as outlined elsewhere in this SAP, some of which, like the primary efficacy analyses, may require data to be complete at particular time points and therefore will only include a subset of the full analysis population with the necessary data available.

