# 9.1 Subject and Cluster Disposition

Summary data for subject disposition and an overview of the time-dependent rates of recruitment will be presented:

- Summary of cluster randomisation to treatment sequence (Table 1.1)
- Summary of time dependent rates of GP practice recruitment (Table 1.1 and Figure 1.1)
- Summary of time dependent rates of patient recruitment (Figure 1.2 and 1.3)
- Summary of patient flow (Table 2.1)
- Subject disposition CONSORT diagram (Figure 2.3)

Questionnaire date for each patient will be recorded at baseline, 6 and 12 months and return rates tabulated:

- Return rates for questionnaires at baseline, 6 and 12 months (Table 2.5).
- Data completeness for SIS emotional domain and SIS handicap domain at 12 months (the coprimary end-points) [where complete data is considered a binary variable for each subject at a given domain] (Table 2.6).

At each stage of the trial, the following variables will be recorded and define whether a patient reached that stage of the trial:

Questionnaire date (dd-mmm-yyyy)

Patients without the above information will have missed a visit, been lost to follow-up or withdrawn due to one of the following:

- Death
- Health deterioration
- Taking part is too burdensome
- 2nd questionnaire not relevant
- 6m questionnaire not relevant
- Left the practice
- No reason given
- Intervention is not relevant
- Will not complete 12m questionnaire
- Not a stroke.

Summary tables of withdrawal will be presented (Tables 4.3 - 4.6).

Intervention progress will be summarised in the following figures and diagrams:

- Breakdown of stroke review progress per recruited intervention GP practice up to [date] (Table 2.2)
- Breakdown of MLAS interest per recruited intervention GP practice up to [date] (Table 2.3)
- Breakdown of the number of stroke survivors attending MLAS by area up to [date] (Table 2.4)
- Progress of enhanced stroke review completion at each intervention GP practice from May 2018 to end of study. GP practice in order of randomisation (Figure 2.1)
- Breakdown of MLAS progress by intervention site over the period May 2018 to [date] (Figure 2.2)

Data concerning the intervention care model will be collected under the following:

- 1) Training
- 2) Enhanced Stroke Review
- 3) MLAS

Process data, fidelity of delivery and receipt will be discussed in Section 10.2.1.

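### The readable plan lets a practice be randomised while reminder replies are still due, and plans no check for consent or baseline SIS received after allocation

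*Protocol*

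**What the plan says.** **When a practice is randomised.** Protocol 6.4: "Once all invitation letters and reminders have been sent out to patients in a practice, the GP practice will be randomised". SAP 6.1: "Once all invitation letters and reminders are sent out to patients in a general practice, the general practice can be randomised". Both triggers are the sending of letters. Neither requires replies to have come back.

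**How long replies may take.** Protocol 6.3.2 sends the reminder 2 weeks after the first mailing. It then says: "If no response is received after a further 4 weeks, no further attempts at contact will be made". That sentence ends the contact attempts. It does not say that a form returned later is refused. The consent form and the primary outcome questionnaire are returned together.

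**When baseline should be collected.** Protocol 9.1: "The primary outcome data will be collected via postal questionnaire at the time of invite to the study prior to Practice randomisation". SAP 6.5 repeats this. The secondary outcome questionnaires are a separate second mailing, which "will also be collected by postal questionnaire after randomisation".

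**Who is analysed and which dates are held.** Under SAP 8.2.1 the full analysis population "comprises all randomised general practices and consented patients within them", with no condition on the consent date. SAP 9.1 says: "Questionnaire date for each patient will be recorded at baseline, 6 and 12 months". The outputs listed there cover recruitment over time, patient flow and return rates. SAP 12 lists a lockdown factor and missing-data analyses.

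**The concern.** The trigger does not by itself secure the plan's own rule that baseline SIS precedes randomisation. A practice can be randomised, and told its arm, while some of its patients still hold an unanswered reminder. Those patients can then join the trial and supply their baseline score after allocation.

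Two things are at stake. First, in a cluster trial the comparison is cleanest when each practice's set of participants is fixed before its arm is known. Late replies could differ between arms. Second, baseline SIS is a covariate in the primary model (SAP 10.1). SAP 6.3 describes the trial as open-label and both co-primary endpoints as subjective, so a baseline score given after allocation could be affected by it. As listed, the outputs would not show a reader whether this happened.

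**Working it through.** **Timeline from the documents**

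| Week from first mailing | Event | Source |
|---|---|---|
| 0 | Invitation, consent form and primary outcome questionnaire sent | Protocol 6.3.2 |
| 2 | Reminder sent to non-responders; randomisation permitted from here | Protocol 6.3.2, 6.4; SAP 6.1 |
| 6 | Contact attempts end | Protocol 6.3.2 |

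Allocation straight after the reminders precedes the end of the reply period by up to 6 − 2 = 4 weeks. With no stated cut-off, a form could arrive later still.

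**Is there a check downstream?**

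- SAP 8.2.1: no date condition on consent.
- SAP 9.1: the listed outputs, as titled, do not compare patient dates with the practice's randomisation date. The baseline questionnaire date is not tied to one of the two mailings.
- SAP 9.3: baseline SIS is tabulated by arm, but late forms are not separated.
- SAP 8.4.2: the oversight committee considers whether the arms are comparable at baseline, again without separating late forms.
- SAP 12: the only date comparison is the 12-month assessment against lockdown.

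**Precision cost of excluding late forms**

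Inputs from Protocol 10.1 and SAP 7: 23 practices per arm, 20 patients each, 20% loss, ICC 0.03, coefficient of variation of cluster size 0.65, significance 2.5%, effect 0.33 SD. The documents do not state whether the test is one- or two-sided; two-sided is assumed, so the critical value is 2.2414. The number analysed per practice is 20 × 0.8 = 16.

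- Design effect: DE = 1 + ((1 + 0.65²) × m − 1) × ICC
- Standard error in SD units: SE = √(2 × DE / (23 × m))
- Power = Φ(0.33/SE − 2.2414)

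The plan's own figure first. At m = 16, DE = 1 + (1.4225 × 16 − 1) × 0.03 = 1.653 and SE = √(2 × 1.653/368) = 0.0948. Power = Φ(1.24) = 89.3%, close to the stated minimum of 90%. With all 20 analysed it is 92.9%.

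Now assume that a share of patients is excluded, evenly over practices and arms:

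| Assumed share excluded | m | Total analysed | DE | SE | SE ratio | Power |
|---|---|---|---|---|---|---|
| 0% | 16.0 | 736 | 1.653 | 0.0948 | 1.000 | 89.3% |
| 5% | 15.2 | 699 | 1.619 | 0.0962 | 1.015 | 88.3% |
| 10% | 14.4 | 662 | 1.585 | 0.0978 | 1.032 | 87.1% |
| 20% | 12.8 | 589 | 1.516 | 0.1015 | 1.071 | 84.4% |

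The shares are assumptions chosen to price the check. They do not estimate how many forms were late.

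**The case against.** The strongest reply is that the documents already state the rule. SAP 6.1 says when a practice can be randomised, which is an earliest point and not a deadline. A team that waits out the reply period satisfies every passage. This stands: the passages can be reconciled, and a reader who inferred an outright contradiction would go too far. What remains is that following the trigger as written can break the baseline rule, and no readable output would show it.

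Second, a reader might infer that late recruitment biased the trial. The documents do not support that. Patient lists, invitations and reminders all precede allocation. Protocol 18.1 keeps identities from the researchers until forms come back. No passage tells patients their arm before they reply. A form received late may have been completed earlier.

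Third, relevant material is not shown. SAP 6.1 says: "The sequence of key study points is summarised in the following flow chart". That chart, the protocol's charts, the invitation pack, the table shells and the data management plan could hold a cut-off or a check. This stands, and it limits the point to the readable text.

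Fourth, a reader might extend the point to the missing-data model and say that it forces equal baseline means in the two arms. The text is not firm enough. The baseline mean printed in SAP 10.1 has no treatment term. SAP 11 lists a treatment indicator, puts baseline among the outcomes and states no equal-baseline constraint. No claim is made here about that model.

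Finally, the baseline date is less obscure than it may look. The withdrawal reasons in SAP 9.1 name the second questionnaire separately, so the team evidently distinguishes the mailings. The SAP need only say which date it means.

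**Conclusion.** The point holds in limited form and is minor. On the readable text, a patient who answers the reminder can consent and give baseline SIS up to 4 weeks or more after the practice was allocated, and nothing planned would identify that patient. The by-arm baseline tables and the committee's review bear on baseline balance but cannot isolate late forms.

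Neither the number of patients affected nor any bias can be derived from the documents. The only size that can be given is the cost of the check: a standard error 2%, 3% or 7% larger if 5%, 10% or 20% were excluded. That rests on the plan's sample-size inputs, a two-sided 2.5% test and exclusions spread evenly. The conclusion would fall away if a document not shown sets a cut-off at randomisation or already contains the check.

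**What to change.** 1. **SAP 9.1.** Tabulate, by arm and practice, the consents and first-mailing (primary outcome) questionnaires dated after the practice's randomisation date. State that the second mailing is not the one meant. The randomisation date is in the audit trail of SAP 6.4 and the questionnaire date is in SAP 9.1. A consent date is implied by SAP 10.1 and 13. No receipt date is named in the readable text, so the team should confirm whether one is held.

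2. **SAP 12.** Pre-specify one sensitivity analysis of both co-primary outcomes, with the same model and 97.5% confidence intervals. Exclude patients whose consent or first-mailing SIS form was received after the practice's randomisation date. Use the date on the form where no receipt date is held. Receipt is the stricter rule: it keeps only patients whose forms were in hand before allocation. Its price is the loss of precision shown above and the possible exclusion of some forms completed before allocation. The programming is light, since SAP 12 already builds a patient-level factor from a date.

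3. **Protocol 6.4 and SAP 6.1.** For any practice not yet randomised, reconcile the trigger with Protocol 9.1 and SAP 6.5. Either randomise after the 4-week reply period or close consent at randomisation. The cost is up to 4 weeks' delay or the loss of late repliers. This probably applies to no practice: the SAP's files are dated April 2020, and it tracks review delivery from May 2018.

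If an unseen document already holds the cut-off or the check, a cross-reference to it in the SAP is enough.

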7.1. Intervention Arm

The new model of care incorporates a multi-factorial package of service aimed at providing a review of patient needs, facilitated self-management of longer-term stroke care needs for survivors and their carers, optimised communication between patients and health and social care services, enhanced communication pathways between the different care services, and increased awareness of and access to national and local community and charity provided services.

Specifically, the intervention will comprise the following components:

1. Structured review of patient needs;

2. A self-management programme (Managing Life After stroke, MLAS) for stroke survivors and their carers;

3. A direct point of contact for stroke survivors and carers at the GP surgery;

4. Enhanced Communication Pathways between General Practice staff and specialist services;

5. Service mapping for stroke related needs;

6. Training for General Practice staff.

7.1.1. Structured Review of Patient Needs

A structured review will be performed by a Practice nurse or other appropriately trained member of the Practice team as part of the regular annual review recommended by current guidelines¹⁰. As part of the review, a 15-item checklist of post-stroke needs (see appendix A) will be sent by the Practice to the stroke survivor in advance. The survivor will be asked to tick all needs which apply to them, and to bring this with them to the appointment. At the review, the patient will be asked which of the ticked items is the most important and they would like to discuss most. Dependent upon time availability at the review, Practice staff will discuss and address up to three key needs identified by the survivor. A blank checklist will also be available in the Practice if needed.

The review will last approximately 20-30 minutes, and include a routine physical check-up based on QoF recommendations (e.g. blood pressure, record of immunisation, and medication review) followed by the discussion of up to three post-stroke needs as identified by the stroke survivor. The expected outcome of the review is an action plan agreed with the stroke survivor on how to address each of the needs identified in the review. A record of the checklist and the agreed action plan (e.g. referrals, agreed actions to be undertaken by the patient) will be kept in the patient records.

The patient will be provided with an information leaflet about the MLAS programme, with instructions on how to get further information from the MLAS team and how to access the programme.

